
**Aim 1. Discover Phase (3 months)** Using iterative and participatory methods, we will work with 10 paraprofessionals who had been trained in telephone-based cognitive behavioral therapy (tCBT) to discover challenges they face in delivery of tCBT, identify areas in the traditional curriculum that supported their skill acquisition, and areas that were missing from the training. Feedback from study team members with expertise in teaching bachelor-level students and other key stakeholders will help inform this process. This information will be used to build the adaptive algorithm in Aim 2. Contribution to the Center: Because the process of educational development includes the identification of competencies that are challenging to learn, data from this phase will be used to inform the Typology of EBPI Targets.

**Aim 2. Design and Build Phase (9 months).** After identifying educational modification targets, and key decisional dilemmas to be built into the program, we will build an Intelligent Tutoring System (ITS) in tCBT via rapid iterative design. The 6 trainees who participated in the *Discover* phase will be actively involved in the *Design/Build* phase, in conjunction with educational experts in tCBT. Contribution to the Center: Data from this phase will be used to inform the Matrix of EBPI Modifications.

[figure not shown]
**Aim 3: Test Phase (18 months).** We will test and compare the addition of an ITS in tCBT to training-as-usual in a small-scale randomized controlled trial. Ten to twelve students will be randomized to the two conditions.

**H1:** The ITS will result in better rating of tCBT usability (AFLA-Q Acceptability, System Usability and User Burden Scales), and student confidence in using tCBT compared to traditional training. **H2:** Students

randomized to the ITS will certify faster (hours in training), and will more competently deliver tCBT elements (number of sessions rated below standard by experts and time to first session rated below standard) than clinicians randomized to traditional training. **H3:** Patients treated by computer-trained students will report better outcomes on functional disability (SDS; Sheehan Disability Scale), and change in depression symptoms over time (PHQ-9 total score) than those treated with traditionally trained students. We will conduct preliminary analysis to determine if change in clinical outcomes is mediated by clinician quality.

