**Training program in telephone-based CBT (tCBT).** tCBT consists of 8 sessions delivered over 10 to 12 weeks. Each session is designed for delivery in 35 - 40 minutes and includes: structured assessment of depressive symptoms (5 min); review of prior session content (5 min); debriefing previous homework assignment (5-10 min); introduction of new material, including in-session examples and exercises (15-20 min); description of the new homework assignment (5-10 min); and a motivational assessment/enhancement exercise focused on the homework assignment (5 min). The current tCBT training program has four key elements: 1) training program content, designed to target competencies of knowledge and attitude, competence in delivering CBT, and fidelity to the treatment; 2) teaching methods, targeting both the cognitive domain (principles and guidelines needed to deliver EBPI) and the affective domain (attitudes and values related to EBPI); 3) simulated case training to practice skills; and (4) teachers and supervisors to provide on-going skill building with actual patients.

Figure 1. DBBT Model for Research Study.

**Study Overview.** To accomplish the aims of the study, this project will be broken down into 3 phases that are tied to each aim of the study: *the Discover phase*, (Aim 1), *the Design and Build phase* (Aim 2), and *the Test phase* (Aim 3; see Fig. 1. For phases 1 and 2, we will work with 10 paraprofessionals who have been trained in tCBT using the traditional mode described above. For phase 3, we will recruit 2 successive cohorts of 5-6 bachelor students from Heritage University and randomize them to the traditional training model and the new adaptive learning method. The study will be conducted over a 2.5 year period during Y01 through Y03. Steps 1 and 2 will be conducted in the first 9 months of the study and Step 3 in the last 15 months (See timeline).

**Phase 1/Aim 1: Discovery (3 months).** The purpose of this phase is to identify key competencies and decisional dilemmas trainees experience when learning tCBT. Drs. [name] and [name] will be responsible for data collection and synthesis in this phase. As is detailed in the **Methods Core**, *Discover* phase data collection involves the identification of user needs, contextual evaluation, and user testing.

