**Phase 3/Aim 3: Test Phase (18 months)**. We will conduct a pilot study comparing the tCBT training that includes the ITS program (from the *Design/Build* phase) to the traditional training program and its impact on time to learning tCBT and competency delivering tCBT. Latino bachelor-level social work and nursing students from Heritage University will be invited in the Spring quarter of their junior year to apply to participate in our specialized program. We will randomize 10-12 students in years 1 and 2 (two successive cohorts of 5-6 students each) during the study and each will work with five patients using tCBT

**Patient eligibility.** Sixty patient participants will be identified through Yakima Valley Farmworker’s Clinic electronic health record. Participants must be 18 years old or older, suffering from mild to moderate depression with PHQ-9 scores of 10-20. Identified patients will be contacted by a Methods Core research assistant to conduct a preliminary screening for eligibility, provide a brief description of the study and obtain informed consent.

**Paraprofessional Data Collection.** After training, paraprofessionals will be assigned a total of 5 cases each to assess paraprofessional capacity to conduct tCBT. Two types of data will be collected—paraprofessional

assessment of tCBT usability, and ability to learn tCBT and maintain competency. To measure **intervention usability**, paraprofessionals will complete the ALFA-Q Acceptability Scale, the User Burden Scale (UBS) and the System Usability Scale (SUS), which are core measures for this center (see **Methods Core** for description of scales). These scales will be collected through the UWAC data portal after initial training in tCBT after they have seen their 5th patient. **Learnability** of the tCBT will be measured as time to reach competency during training. To measure **sustained competency**, paraprofessionals will collect audio recordings of patient sessions for review by experts. Drs. [name] and [name] will conduct these reviews using the Cognitive Therapy Scales (CTS) adapted to apply to structured, manualized telephone CBT. The CTS utilizes a 7-point rating scale (0 = *poor*, 6 = *excellent*) and has been used to assess the competence of paraprofessional therapists. Sustained competency will be defined by (1) time to first session rated below average and (2) number of sessions rated below average.

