**Data Analysis.** Aim 3 focuses on pilot feasibility data to inform a larger (future) clinical trial comparing ITS-based training in tCBT to training-as-usual (TAU). Thus, analyses do not focus on hypothesis-driven inferential statistics but on descriptive statistics, graphical summaries, and basic effect sizes. H1: Usability. Differences in clinician-reported usability between ITS training and TAU will be plotted using a dotplot and tested using a *t*-test using the ALFA-Q, SUS, and UBS as dependent variables. H2: Fidelity/Competence: A similar strategy (dotplot, *t*-test) will be used with number of hours to reach certification. Number of sessions with CTS scores in competent range will be summarized as proportions, both by clinician and by treatment. Between-group differences will be tested with a 2-sample proportion test. (Future analyses with larger sample size will use a generalized linear mixed model approach to account for the nested data.) H3: Patient-Reported Outcomes. Histograms and kernel density estimates will be plotted by treatment condition to explore differences on depression outcomes (PHQ-9 total score) and overall daily functioning (SDS). Descriptive statistics (*M* and *SD*) will also be examined by clinician and by treatment, using Cohen's *d* as an effect size summary. A *t*-test will be used to examine treatment differences in patient outcomes. Of ultimate interest is whether the modified training protocol (i.e., ITS vs. TAU) has its impact on patient outcomes through enhanced learnability via clinician competence/fidelity. We will use graphical summaries of the data to explore the relationships that are consistent with mediation (e.g., correlation of usability with patient outcomes [b pathway], and treatment differences on patient outcomes with fidelity partialled out [c' pathway']). The primary focus here is whether the data and relationships appear consistent with mediation, as opposed to a formal test, which will be dramatically under-powered.

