**Power and Sample Size.** Sample sizes for Aims 1 and 2 were based on estimates from the user-centered design literature on necessary number of participants to capture critical design information, where the recommendation is 5-10 end users. Aim 3 is focused on gathering information (feasibility, recruitment and retention rates, response and attrition rates, etc.) for a future R01 application. Thus, the sample size was set primarily for practical reasons and driven by estimated effect sizes rather than hypothesis testing..

**Timeline.** This study will begin in Y02 of the Center. The *Discover* phase activities will be completed in 3 months. The *Design/Build* phase will be completed in 9 months. The *Test* phase will take 18 months, of which identification and training of clinicians in the two interventions will take approximately 2 months for each cohort. Patient recruitment and data collection will take 10 months. Data analysis will take 3 months.

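### Students are randomised in two successive cohorts, but no H1-H3 comparison uses cohort; this costs some precision and is cheap to correct

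*Combined protocol and SAP*

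**What the plan says.** Three places describe the allocation. Aim 3 in the Specific Aims says: "Ten to twelve students will be randomized to the two conditions". The Study Overview says: "we will recruit 2 successive cohorts of 5-6 bachelor students from Heritage University and randomize them to the traditional training model" and the adaptive method. The Test Phase section says: "We will randomize 10-12 students in years 1 and 2 (two successive cohorts of 5-6 students each) during the study". The Timeline treats the cohorts as separate training rounds: "identification and training of clinicians in the two interventions will take approximately 2 months for each cohort". No allocation ratio is stated, and no blocking or stratification by cohort.

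The Data Analysis section sets out these comparisons:

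- H1: "Differences in clinician-reported usability between ITS training and TAU will be plotted using a dotplot and tested using a" t-test, on the ALFA-Q, SUS and UBS.
- H2, training time: the same dotplot and t-test "will be used with number of hours to reach certification".
- H2, competent sessions: proportions by clinician and by treatment, then "Between-group differences will be tested with a 2-sample proportion test".
- H3: means and SDs by clinician and by treatment, with Cohen's d; a t-test "will be used to examine treatment differences in patient outcomes".

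Cohort is not a covariate, a stratum or a descriptive grouping in any of them. A mixed model is mentioned only for later, larger studies, and its stated purpose is nesting, not cohort. The section also says that the emphasis is on description and effect sizes rather than inference.

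**The concern.** The cohorts are different student groups, trained separately in successive years. If they differ in, say, hours to certification, a pooled two-group comparison handles the difference in two ways. First, it counts the difference as random variation within each arm, which widens the interval and enlarges the SD used to standardise an effect. Second, if one arm has a larger share of cohort 1 than the other, part of the difference is read as a training effect. A cohort of five cannot split evenly. Because restriction by cohort is not stated, a cohort of six need not split 3:3 either.

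With 10-12 students there is little precision to spare. The effect estimates are also what this pilot is meant to pass to the larger trial.

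**Working it through.** **The plan's own figures.** 2 × 5 = 10 and 2 × 6 = 12 students. At five patients each, 12 × 5 = 60 patients, which matches the stated sixty (10 students would give 50). There is no power calculation, alpha, SD or effect size to reproduce.

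**Assumptions.** Two-sided 0.05; within-cohort SD of 1; a cohort gap of D SD, shown from 0 to 1; allocation as near 1:1 within cohort as possible. None of these is in the documents. The simulated figures come from 40,000 runs per case, comparing the two-group t-test with a linear model of arm plus cohort.

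**Share of the gap that enters the arm difference** = (share of the ITS arm from cohort 1) − (share of the usual-training arm from cohort 1).

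| Layout (ITS:usual, cohort 1 then 2) | Calculation | Share |
|---|---|---|
| 5+5, 3:2 then 2:3 | 3/5 − 2/5 | 20% |
| 5+6, 3:2 then 3:3 | 3/6 − 2/5 | 10% |
| 6+6, 3:3 twice | 3/6 − 3/6 | 0% |
| 5+5, 3:2 twice | 3/6 − 2/4 | 0% |

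If only the arm totals were fixed, 12 students would split 3:3 in both cohorts with probability 20 × 20 / 924 = 43%. A 4:2 then 2:4 split would carry 4/6 − 2/6 = 33% of the gap.

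**Error term, 12 students, 3:3 twice.** Each arm has three students from each cohort, so the gap adds 6 × (D/2)² = 1.5D² to each arm's sum of squares, or 3D² over 10 df. The expected residual variance is 1 + 0.3D². The standard error multiplier is the same with or without adjustment, so the width ratio, unadjusted to adjusted, is 2.228 × √(1 + 0.3D²) / 2.262:

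- D = 0: 0.985 (1.5% narrower)
- D = 0.5: 0.985 × √1.075 = 1.02 (2% wider)
- D = 1: 0.985 × √1.3 = 1.12 (12% wider)

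Break-even: 1 + 0.3D² = (2.262/2.228)² = 1.031, so D is about 0.32. Simulated mean half-widths agree: 1.27 SD adjusted throughout, against 1.25, 1.30 and 1.43 SD unadjusted.

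**Error term, 10 students, 3:2 then 2:3.** The gap adds (3 × 2/5)D² = 1.2D² per arm, or 2.4D² over 8 df, which is again 0.3D². Critical t goes from 2.306 to 2.365. Simulated mean half-widths, unadjusted and adjusted:

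- D = 0: 1.414 and 1.473; adjusting costs 1.473/1.414 = 1.04
- D = 0.5: 1.467 and about 1.475; close to break-even
- D = 1: 1.61 and 1.47; 1.61/1.47 = 1.095, about 10% wider unadjusted

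With a true arm effect of 1 SD and D = 1, the unadjusted mean estimate in this layout is 0.80 or 1.20 SD, depending on which way the split fell. The adjusted mean is 1.00 SD.

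**Test behaviour at D = 1.** With 12 students at 3:3, the unadjusted t-test rejects 2.8% of the time under no effect. For a 1 SD effect its power is 26%, against 34% adjusted. With 10 students at 3:2 then 2:3, the unadjusted rejection rate under no effect is 3.5%. The test is conservative in both layouts.

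**The case against.** The strongest reply is that this is a pilot. The plan makes no power claim, sets the sample on practical grounds, puts description first and does not plan a confidence interval. The documents give no cohort gap, and the 12% figure needs an assumed gap of 1 SD. At 0.5 SD the gain with 12 students is only 2%, and with 10 students there is none. All of that stands and keeps the priority modest. It does not remove the point, because the t-tests are still planned and the raw differences and SDs that feed the effect sizes are affected too. At D = 1 a student-level SD rises by √1.3 = 1.14, so a standardised difference of 1.0 would read 1/1.14 = 0.88.

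A second reply is that the calculations cover only 10-12 student-level values. That is correct. Nothing was computed for the session-level proportion test or the patient-level t-test, and the figures should not be carried over to them.

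Three stronger readings are tempting but unsupported:

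- A reader might infer that the pooled analysis is biased. Under randomisation the direction of any cohort imbalance is a matter of chance, so the 0.80 and 1.20 above are two sides of the same lottery.
- A reader might infer that the cohorts' patients are seen in different seasons. The documents do not say so. Students are invited in the spring quarter, and the Timeline gives a single 10-month span for patient recruitment and data collection.
- A reader might infer that cohort is the only known grouping among students. The Test Phase section also mixes social work and nursing students. What distinguishes cohort is that it is built into enrolment and randomisation.

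**Conclusion.** The point holds as a modest improvement. Cohort is part of how students are enrolled and randomised, yet it is absent from every planned comparison. The consequence is lost precision and a conservative t-test in near-even layouts, with between 0% and 20% of any cohort gap entering the arm difference by chance. It would be wrong to read this as the whole gap entering whenever a cohort of five splits 3:2; two such cohorts split the same way contribute nothing.

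For student-level outcomes, adjustment pays once the gap exceeds about 0.3 SD with 12 students, or about 0.5 SD with 10 split 3:2 then 2:3. These thresholds rest on near-even allocation within cohort, a common SD and a two-sided 0.05 level, all assumed here. Whether the real gap lies above or below them cannot be told from the documents.

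**What to change.** In the Data Analysis section:

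1. For the ALFA-Q, SUS, UBS and hours to certification, estimate the arm difference with cohort as a two-level fixed factor, and mark cohort by symbol on the dotplots.
2. For competent-session proportions and for PHQ-9 and SDS outcomes, report the weighted average of the two within-cohort arm differences beside the planned summary. This does not deal with the nesting of sessions and patients within students, and no gain in precision is claimed for it.
3. State which SD standardises Cohen's d, the pooled SD or the within-cohort SD, since the two differ if the cohorts differ.

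The cost is a few lines of text and no new data. For student-level outcomes it is one degree of freedom, with an interval about 1.5% wider (12 students) to 4% wider (10 students, 3:2 then 2:3) if the cohorts turn out not to differ. The choice is best fixed before outcomes are seen.

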### **Sources of Materials.**

**Patients.** Phase 3 enrolled patients will complete an online survey in English or Spanish at baseline and post treatment. Clinic staff and UW staff will have access to participant identifiers (e.g. patient name, email, address, alternative contact information) for the purpose of reaching the participant to complete the baseline survey, to follow-up with them for post treatment surveys and to pay them for completed surveys. Surveys will be conducted the UWAC data portal that directly enters responses into an electronic dataset, eliminating paper forms that might get lost or misplaced. The electronic dataset will be stored on UW's Amazon Web Services HIPAA Compliant server. Participant data is automatically sent to the AWS secure server behind established university firewalls via custom, encrypted API calls in JSON format. A MongoDB database is used to capture all data, with access only through administrator privileges that require a unique username and password. Specific summary data extracted from the JSON is also written in parallel to a MySQL database for additional summary statistics used to populate participant-specific dashboards to provide an ongoing view of their progress in the study.

**Phase 1 and 2 data.** Qualitative interviews regarding their experience with the training program will be conducted via interactive video and be audio recorded. The UWAC discovery team will have access to provider identifiers (e.g. provider name, phone number) for the purpose of scheduling interview. Voice recordings are considered identifying information and the transcriptionist will have access to this for purposes of creating a transcript for analysis.

**Audio Recordings.** Audio recordings of participant and clinician interaction in Phase 3 to study clinician competency will be uploaded to a HIPAA-compliant FTP (file transfer protocol) server at the University of Washington (UW) so that they can be reviewed. This system is password protected and each recording has a designated recipient and only that person can access it. The system is further designed to automatically delete recordings after a pre-determined number of days if not accessed so they do not linger on the system. Once the recordings are reviewed UWAC staff will insure that no identifiable information remains on the transcript before analysis.

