data safety in general. They will acknowledge that any lapse could result in disciplinary action or termination. In addition, the proposed project will adhere to the following general rules of data safety: 1) all staff will sign a written commitment to maintain an atmosphere of confidentiality, which will include not discussing confidential study information with anyone outside the study team and not attempting to learn the identity of an individual participant; 2) all data will be marked only by a non-identifying ID number; 3) all identifying information (consent forms, contact information for follow-up interviews) will be kept separate from data gathered from participants and kept in password-protected files in password-protected computers or systems; 4) non-study personnel will at no time be permitted to view identifying information; 5) all electronic data containing identifiers will be maintained with password protection, 6) all participants must understand, agree, and sign a consent form before participating and will be provided a copy of the consent form with instructions about how to contact a university official responsible for research oversight with any questions or concerns; 7) strict adherence to a participant's right to withdraw or refuse to answer questions will be maintained; and 8) participants will be provided with a summary of study results upon verbal or written request. In addition, qualitative interviews will be scheduled ahead of time to facilitate participant privacy in case friends or family members (who may be unaware that the individual is participating in a study) may be curious as to why the participant is being contacted. We will train research assistants to tactfully avoid answering such questions. **For student participants:** Data from this study will not be shared with university or clinic staff. Performance as tCBT clinician, and performance during training will be handled as usual, through supervision, but will not influence student grades.

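### The CTS raters are not masked to training arm or balanced across arms, so the competence part of H2 is open to rater bias

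*Combined protocol and SAP*

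**What the plan says.** The Specific Aims (Aim 3, H2) give the competence part of H2 as "number of sessions rated below standard by experts and time to first session rated below standard". The other part is hours in training.

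Under Approach, Phase 3/Aim 3, Paraprofessional Data Collection, "paraprofessionals will collect audio recordings of patient sessions for review by experts". Two doctors, whose names are removed, "will conduct these reviews using the Cognitive Therapy Scales", adapted for structured telephone CBT. "The CTS utilizes a 7-point rating scale", running from 0 to 6. The same paragraph ends: "Sustained competency will be defined by (1) time to first session rated below average and (2) number of sessions rated below average".

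Sources of Materials, Audio Recordings, describes the file server: "each recording has a designated recipient and only that person can access it". Recordings that nobody opens are deleted automatically after a set number of days. Staff check transcripts for identifying information, but only after the review.

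Protection of Confidentiality requires data to carry only an ID number that does not identify the participant.

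Data Analysis summarises sessions in the competent CTS range as proportions, by clinician and by treatment, and compares arms with a two-sample proportion test. It contains no rater term.

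**The concern.** Both sustained-competency measures come from expert judgement on a subjective scale. Two routes to bias are left open.

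- **Knowledge of arm.** A rater who knows, or can work out, how a student was trained may score that arm more generously or more harshly without intending to.
- **Rater severity.** Two raters seldom use a scale identically. If each recording is scored by one person and the share going to each rater differs between arms, the difference in severity is read as a difference in training.

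Either one moves the estimate itself, so a mainly descriptive analysis is not protected. The pilot is meant to inform an R01 application, and a distorted competence difference would pass into it. It would also enter the exploratory mediation plots where fidelity is partialled out.

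**Working it through.** The plan states no figure on this point, so there is nothing to reproduce. The check is a reading of the provisions, followed by an illustration of size.

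**1. Could an existing provision do the job?**

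- *ID-number rule (Protection of Confidentiality).* It protects identity in the data. It does not say that the rater is kept unaware of arm.
- *Designated recipient (Audio Recordings).* This controls access. It suggests one rater per recording and does not say how that rater is chosen.
- *Transcript check (Audio Recordings).* It happens after scoring and concerns personal identifiers, not arm.
- *Methods Core reference (Paraprofessional Data Collection).* It is cited for the usability scales, not for CTS rating.
- *Data Analysis.* There is no rater term, double rating or agreement check.

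None of these masks arm or balances raters across arms.

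**2. Leniency towards one arm (assumed values).** Take approximately normal CTS scores, no true arm difference, a true below-average rate p, and leniency of d standard deviations towards ITS. The observed ITS rate is Φ(z_p − d).

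| True rate p | z_p | d = 0.25 | d = 0.50 |
|---|---|---|---|
| 30% | −0.524 | Φ(−0.774) = 21.9% | Φ(−1.024) = 15.3% |
| 20% | −0.842 | Φ(−1.092) = 13.7% | Φ(−1.342) = 9.0% |

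At 30% the spurious gap is 30 − 21.9 = 8.1 to 30 − 15.3 = 14.7 percentage points. At 20% it is 6.3 to 11.0 points.

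**3. Unequal split between raters (assumed values).** Let the raters differ by g in the proportion of sessions they call competent, and let the lenient rater's share of recordings differ between arms by w. The spurious arm difference is w × g. With g = 10 points:

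- w = 20 points: 0.2 × 10 = 2 points
- w = 50 points: 0.5 × 10 = 5 points
- w = 100 points: 1.0 × 10 = 10 points
- w = 0 (balanced split): 0 points

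**4. What the planned test would make of a 5-point shift.** If every session is recorded and rated, 10 to 12 students × 5 cases × 8 sessions gives 400 to 480 recordings, or 200 to 240 per arm with equal arms. Assume a true competent rate of 80% in both arms, scored as 85% under ITS. With 200 per arm:

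- SE = √(0.80 × 0.20/200 + 0.85 × 0.15/200) = 0.0379
- 0.05/0.0379 = 1.32
- chance that a two-sided 0.05 test favours ITS = 1 − Φ(1.96 − 1.32), about 26%

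With 240 per arm it is about 30%. Without the shift it would be 2.5% in that direction. This treats sessions as independent, as the planned test does; clustering within students would change the figures and is a separate matter.

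**The case against.** The strongest reply is that this is a small pilot. Data Analysis disclaims a focus on hypothesis testing, Power and Sample Size presents Aim 3 as gathering feasibility information, and the mediation work is graphical, with usability rather than CTS in its example of the b pathway. The illustrative leniency, base rates and rater differences have no source in the documents; they show only that an assumed bias produces a bias. All of this stands, and it limits the consequence. It does not remove the point, because the plan still compares the arms on these ratings and the descriptive estimates would be distorted too.

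Three stronger readings are tempting, and the documents do not support them.

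- *The raters built the ITS or supervise the students.* Their names are removed and their other roles are not given. The statement that "performance during training will be handled as usual, through supervision" belongs to a sentence about keeping student performance away from grades; it does not connect supervision with CTS rating.
- *Nothing conceals who the student is.* The ID-number rule exists, and the documents do not say how recordings are labelled when they reach a rater. What is missing is masking to arm.
- *All of H2 is affected.* Hours to certification is not stated to rest on these reviews, although who judges certification is not described.

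There are also practical limits. With 10 to 12 students a voice may be recognised, and because each session reviews earlier content, its place in the course may be audible.

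**Conclusion.** The concern holds for the CTS-based part of H2: time to first, and number of, sessions rated below average. The plan has two experts make subjective ratings, does not mask them to arm, and does not balance recordings between them. Bias is possible; nothing in the documents shows that it occurred or would favour ITS.

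The size cannot be derived from the documents. On the assumptions above, moderate leniency gives a spurious gap of roughly 6 to 15 percentage points, and a 10-point difference between raters gives up to 10 points, depending on how unevenly recordings are shared. These are illustrations, not estimates. The point does not invalidate the pilot. The change is worth making because it is cheap and protects a comparison that the plan intends to report.

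**What to change.** Add a short paragraph to Paraprofessional Data Collection:

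1. UWAC staff give each recording a random code that shows neither arm nor student. They keep the key, including session order, so that time to first below-average session can be computed later.
2. Within each cohort, recordings are released in random order with the arms mixed, in batches short enough to be opened before the server's automatic deletion. Cohorts are not mixed: they are successive, and holding the first cohort's recordings for the second would risk losing them.
3. Recordings are assigned at random to the two existing raters, stratified by student, so that both raters score part of each student's work. With 5 × 8 = 40 recordings per student, that is 20 each. Rater is then balanced by arm.
4. CTS scores are locked before they are linked to arm.
5. If a rater also trains or supervises a student, this is recorded, and the rater-by-arm balance is reported.

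The cost is staff time for coding and release; no extra raters or ratings are needed. Masking will be partial, since a voice or a mention of the ITS may reveal the arm. The balanced split still removes confounding of rater severity with arm, though not leniency towards an arm that a rater has recognised. Agreement between raters on the same recording remains unmeasured.
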